5.5 General Concomitant Medication and Supportive Care Guidelines

Because the potential for interaction of ONC201 with other concomitantly administered drugs through the cytochrome P450 system is not known, the clinical source documentation will capture the concurrent use of all other drugs, over-the-counter medications, and/or alternative therapies. The Sponsor should be alerted if the patient is taking any agent known to affect or with the potential to affect selected CYP450 isoenzymes.

Any medication taken by a subject during the course of the study and the reason for its use will be documented in the clinical source documentation.

5.6 Criteria for Taking a Participant Off Protocol Therapy

Duration of therapy will depend on individual response, evidence of disease progression and tolerance. Treatment will be discontinued for progression of disease, intolerance (defined as NCI Common Terminology Criteria for Adverse Events (CTCAE) version 5.0 Grade 4, Grade 3, or intolerable Grade 2 toxicity that does not return to Grade 1 or baseline after 3 week interruption of treatment or reduction of dose) despite dose modification, or patient withdrawal. A patient who experiences a DLT is able to remain on study at a reduced dose (see section 6), if deemed by the physician to be safe and beneficial for the patient to continue.

In the absence of treatment delays due to adverse events, treatment may continue until one of the following criteria applies:

- Confirmed radiographic disease progression. Treatment beyond radiographic progression, with prior agreement by the Sponsor's medical representative and investigator, may be allowed if considered in the best interest of the patient. This may include the addition of bevacizumab and/or radiotherapy as clinically indicated

and per local standard practice.

- Intercurrent illness that prevents further administration of treatment,
- Unacceptable adverse event(s),
- Treatment interruption for more than 3 consecutive weeks due to intolerance despite appropriate dose modification,
- Participant decides to withdraw from the study, or
- General or specific changes in the participant's condition render the participant unacceptable for further treatment in the opinion of the treating investigator,
- Global deterioration of health-related symptoms,
- Protocol non-compliance,
- Pregnancy,
- Lost to follow-up, or
- Study termination by Sponsor.

If a patient does not return for a scheduled visit, every effort should be made to contact the patient. In any circumstance, every effort should be made to document patient outcome, if possible. The Investigator should inquire about the reason for withdrawal, request that the patient to return all unused investigational product(s), request the patient to return for a final visit, if applicable, and follow-up with the patient regarding any unresolved adverse events.

If the patient withdraws from the trial and also withdraws consent for disclosure of future information, then no further evaluations should be performed and no additional data should be collected. The Sponsor may retain and continue to use any data collected before such withdrawal of consent.

5.7 Duration of Follow Up

After documented disease progression each subject will be followed by telephone or medical record review for overall survival. When available, subsequent cancer treatment information and disease imaging up to two years after end of treatment visit will be obtained for patients after discontinuing ONC201 treatment.

Participants will be followed up for survival until one of any of the following criteria apply: lost to follow-up, withdrawal of consent, death.

5.8 Criteria for Taking a Participant Off Study

Patients will be removed from study when any of the criteria listed in Section 5.4 applies. The reason for study removal and the date the patient was removed must be documented in the clinical source documentation.

Severe adverse events, availability of new adverse toxicology in animals, and financial difficulties due to withdrawal of funds may result in stopping the trial. An investigator, Sponsor, or IRB may take such actions. If the trial is terminated for safety reasons, subjects will be notified immediately and assured that appropriate treatment and follow-

up will be available. If an investigator terminates the trial, the investigator will inform the Sponsor, subjects, and IRB about the reason for such action. Similarly, if the Sponsor terminates the trial, it will inform the investigators, the IRB, and the subjects of the reason for such an action. Similar notifications will be sent by the IRB if it takes such an action.

The reason for taking a participant off study, and the date the participant was removed, must be documented in the clinical source documentation.

6. DOSING DELAYS/DOSE MODIFICATIONS

The descriptions and grading scales found in the revised NCI Common Terminology Criteria for Adverse Events (CTCAE) version 5.0 will be utilized for dose delays and dose modifications

Below are dose modifications (Table 6.1) for adverse events that are attributable to study drug. If a patient experiences other adverse events, or several adverse events and there are conflicting recommendations based on Grade, the investigator will use the recommended dose adjustment that reduces the dose. Dose modifications will be made based on an adverse event that occurs any time during a cycle.

Criteria for disrupting treatment, dose modification, or discontinuation are listed in Table 6.1. Dose modifications are per the clinical judgment of the investigator and agreement of the subject, the treatment will be resumed according to the table below. Dose modification may not be required for adverse events that are clinically manageable.

Table 6.1 Dose adjustment rules for Adverse Events (AEs) Attributable to Study Drug. Alopecia does not require dose adjustments.

CTCAE Grade	Management/Next Dose for ONC201
≤ Grade 2	No change in dose
Grade 3 or 4*	Hold until ≤ Grade 2. If resolved to ≤ Grade 2 within 3 weeks, resume dosing at 500mg if previously dosed at 625mg or resume dosing at 375mg if previously dosed at 500mg.**
*Patients requiring a delay of >3 weeks should go off protocol therapy. Patients with grade 3 neutropenia associated with fever should also go off therapy. ** Patients requiring > two dose reductions should go off protocol therapy.	

Participants who experience an adverse event that requires a treatment delay or dose reduction should be monitored with appropriate laboratory testing or other clinical evaluation at least weekly until resolution; if the adverse event does not resolve within 3 weeks, the interval for testing may be reduced after consultation and written approval by Sponsor.

For holds for reasons other than treatment related toxicities, if the participant does not meet criteria to resume treatment within 6 weeks of the event precipitating the hold, the study agent(s) may be restarted with approval from the Sponsor, as long as there has been no significant evidence of disease progression (e.g., by clinical findings, symptoms, tumor markers) during the treatment interruption.

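### The Table 6.1 footnote takes Grade 3 neutropenia with fever off therapy but does not name Grade 4, so the more severe event has the lighter written rule

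*Protocol*

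**What the plan says.** Section 6 of the protocol sets the scope of the table: "Below are dose modifications (Table 6.1) for adverse events that are attributable to study drug". Table 6.1 has two rows. At Grade 2 or lower the dose stays the same. For Grade 3 or 4, treatment is held until the event is Grade 2 or lower. If it recovers to "Grade 2 within 3 weeks, resume dosing at 500mg if previously dosed at 625mg or resume dosing at 375mg if previously dosed at 500mg".

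The Grade 3 or 4 row carries two footnotes:

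- The single-asterisk footnote takes a patient off protocol therapy when the delay exceeds 3 weeks. It then adds: "Patients with grade 3 neutropenia associated with fever should also go off therapy".
- The double-asterisk footnote reads: "Patients requiring > two dose reductions should go off protocol therapy".

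The surrounding text of Section 6 leaves room for discretion: "Dose modifications are per the clinical judgment of the investigator and agreement of the subject". Section 5.6 gives further grounds for stopping. These include an intolerance definition, which lists Grade 4, Grade 3 and intolerable Grade 2 events and turns on non-recovery, and a general criterion for unacceptable adverse events. The SAP contains no dosing rules.

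**The concern.** The row covers both grades, but its fever exception covers only the lower one. A stop rule for a given toxicity should become no lighter as the grade rises. Here the written instruction for Grade 3 neutropenia with fever is to end treatment, while for Grade 4 with fever the only written instruction is the general one, hold and then resume at a reduced dose. Nothing in the protocol explains the difference.

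What is at stake is the safety of individual patients and consistency between sites. Table 6.1 is where sites look up the action for drug-related toxicity. The trial is multi-center, and doses after Cycle 1 Day 1 may be taken at home, so a safety stop should not depend on each site inferring what the footnote meant.

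**Working it through.** No sample size, power or error rate enters this point. The check is to follow each event through the rules as written and then see whether any other provision closes the gap.

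**The two events under Table 6.1** (attributable to ONC201, patient on 625 mg)

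| | Grade 3 neutropenia with fever | Grade 4 neutropenia with fever |
|---|---|---|
| Row that applies | Grade 3 or 4 | Grade 3 or 4 |
| Named in the fever footnote | Yes | No |
| Written action | Off therapy | Hold until Grade 2 or lower |
| If recovered within 3 weeks | Still off therapy | Resume at 500 mg (500/625 = 80% of the dose) |
| If not recovered within 3 weeks | Off therapy | Off therapy |

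The two columns differ only when the event recovers in time. In that case the more severe event may resume and the less severe one may not.

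**Other provisions that might supply a Grade 4 stop**

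1. *Intolerance definition, Section 5.6.* After naming Grade 4 and Grade 3, it closes with the lowest grade that it treats as intolerable and the condition for stopping: "Grade 2 toxicity that does not return to Grade 1 or baseline after 3 week interruption of treatment or reduction of dose) despite dose modification". Read naturally, the non-recovery condition applies to all the listed grades, so a Grade 4 event that does recover is not caught. If Grade 4 were instead a trigger on its own, Section 5.6 would contradict the Grade 3 or 4 row of Table 6.1, and the text would still need correcting.
2. *Dose-limiting toxicity sentence, Section 5.6.* A patient with such a toxicity may continue at a reduced dose if the physician considers this safe and beneficial. That is a condition on continuing, not a stop, and for the reduced dose it points back to Section 6. The protocol text provided does not define the term.
3. *Unacceptable adverse events, Section 5.6.* Once an event is judged unacceptable, treatment ends. The judgment is left open, and no grade or type of event is named.
4. *Investigator judgment, Section 6.* It allows a stop but can also go the other way. The same paragraph says that manageable events may need no modification and that treatment resumes according to the table.
5. *Conflict rule, Section 6.* When recommendations conflict, the one that lowers the dose is used. It points to dose reduction, not to discontinuation.
6. *Limit on dose reductions, Table 6.1.* It acts only when more than two reductions are needed, so it does not reach a first Grade 4 event with fever.

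None of the six tells the site to stop for Grade 4 neutropenia with fever that recovers within 3 weeks.

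**The case against.** The strongest reply is that this is a slip of wording and no investigator would act on it. The footnote hangs on a row for Grade 3 or 4 and adds a stricter exception to it. A clinician who must stop at Grade 3 with fever has no sensible reason to resume after Grade 4 with fever. Resumption is never automatic, because Section 5.6 requires the physician to find it safe and beneficial after a dose-limiting toxicity, and Section 6 leaves dose modification to judgment. The event may also be rare: Section 2.3 reports no drug-related toxicity above Grade 1 in the phase I dose escalation up to 625 mg.

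Most of this stands. The intended meaning is probably Grade 3 or worse, and discretion reduces the practical risk. It does not turn the text into a stop rule. The phase I evidence comes from ten evaluable patients dosed every 3 weeks, which says little about weekly dosing.

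A reader might infer two stronger points, which the documents do not support.

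- *A count of episodes.* One could walk the dose ladder (625, 500, 375 mg) and conclude that a patient may have repeated Grade 4 episodes with fever before the limit on reductions applies. That is a constructed worst case. It leaves out the Section 5.6 condition of return to Grade 1 or baseline, under which a patient who stays at Grade 2 after the dose modification would go off therapy sooner.
- *A conflict over Grade 2.* The lower row says "No change in dose", while Section 5.6 mentions dose reduction in a sentence that includes intolerable Grade 2 toxicity. That sentence can be read distributively, with reduction for Grade 3 or 4 and interruption for Grade 2. The table does not forbid interruption, and Section 6 leaves modification to judgment. No defect is shown there.

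**Conclusion.** The concern holds as an error in one written safety rule. For attributable neutropenia with fever that recovers to Grade 2 or lower within 3 weeks, the protocol tells sites to stop at Grade 3 and, read literally, lets them resume at a reduced dose after Grade 4. The likely cause is a drafting omission, and the discretionary provisions together with the Section 5.6 non-recovery rule limit the harm.

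The conclusion rests on a literal reading of the footnote and on the absence of any other rule for this event in the protocol text provided. It does not depend on how often the event occurs, which the documents do not allow one to estimate. Nothing is claimed about the number of episodes, the efficacy endpoints, the sample size or the error rates. Because the subject is a safety stop and the correction is almost free, it should be made.

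**What to change.** In the single-asterisk footnote to Table 6.1, replace grade 3 with Grade 3 or higher in the sentence on neutropenia with fever, and leave the rest of the sentence unchanged. The hold-and-resume row and the limit on dose reductions can stay as they are.

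The cost is a change of a few words in one footnote, made in a protocol amendment and passed on to the sites. It needs no extra visits, data or patients and no change to the SAP.

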7. ADVERSE EVENTS: LIST AND REPORTING REQUIREMENTS

An adverse event is defined as any untoward medical occurrence in a patient or clinical investigation subject administered a pharmaceutical product and which does not necessarily have to have a causal relationship with this treatment. An adverse event can therefore be any unfavorable and unintended sign (including an abnormal laboratory finding, for example), symptom, or disease temporally associated with the use of a medicinal product or protocol-specified procedure, whether or not considered related to the medicinal product or protocol-specified procedure. Any worsening (i.e., any clinically significant adverse change in frequency and/or intensity) of a preexisting condition that is temporally associated with the use of the ONC201, is also an adverse event.

Changes resulting from normal growth and development that do not vary significantly in frequency or severity from expected levels are not to be considered adverse events. Examples of this may include, but are not limited to, onset of menses or menopause occurring at a physiologically appropriate time.

Adverse events may occur during the course of the use of ONC201 product in clinical trials or within the follow-up period specified by the protocol, from overdose (whether accidental or intentional), from abuse and from withdrawal. Adverse events may also occur in screened subjects during any pre-allocation baseline period as a result of a protocol-specified intervention, including washout or discontinuation of usual therapy, diet, placebo treatment or a procedure.

Progression of the cancer under study is not considered an adverse event.

All adverse events will be recorded from the time of initiation of study therapy through completion of the safety follow-up period. This period is from the time of discontinuation of ONC201 treatment until 30 days after discontinuation of treatment or until initiation of a new post-discontinuation anticancer treatment, whichever comes first. If a patient initiates a new anticancer treatment within 30 days after discontinuing ONC201, the safety follow-up visit should be conducted prior to the start of that new line of therapy, if possible. Regardless of the end of the safety follow-up period or any new therapies, all SAEs that are deemed at least possibly related to ONC201 should be reported to the Sponsor and followed to resolution.

Both adverse events and Serious Adverse Events will not be collected for subjects during the pre-screening period (for determination of archival tissue status) as long as that subject has not undergone any protocol-specified procedure or intervention. If the subject requires a blood draw, fresh tumor biopsy etc., the subject is first required to provide consent to the main study and AEs will be captured according to guidelines for standard AE reporting.

All SAEs and AEs related to study treatment or leading to discontinuation should be followed until resolution, stabilization, the event is otherwise explained, or the participant is lost to follow-up.

Adverse event (AE) monitoring and reporting is a routine part of every clinical trial. All Adverse Events regardless of seriousness or relationship to the Investigational Product will be recorded in the Case Report Forms. Serious Adverse Events should be reported per the requirements described in Section 7.1.

7.1 Reporting of Serious Adverse Events

Serious Adverse Events: A serious adverse event is any adverse event occurring at any dose or during any use of ONC201 that:

- Results in death;
- Is life threatening;
- Results in persistent or significant disability/incapacity;
- Results in or prolongs an existing inpatient hospitalization;
- Is a congenital anomaly/birth defect;
- Is a new cancer (that is not a condition of the study);
- Is associated with an overdose;
- Is another important medical event

Progression of the cancer under study is not considered an adverse event.

Any serious adverse event, or follow up to a serious adverse event, including death due to any cause other than progression of the cancer under study that occurs to any subject from the time of initiation of therapy through 30 days following cessation of treatment, or the initiation of new anti-cancer therapy, whichever is earlier, whether or not related to ONC201, must be reported within 24 hours to the Sponsor.

Additionally, any serious adverse event, considered by an investigator who is a qualified physician to be related to ONC201 that is brought to the attention of the investigator at any time outside of the time period specified in the previous paragraph also must be reported immediately to the Sponsor.

SAE reports and any other relevant safety information are to be forwarded to the Sponsor email noted on the Sponsor Contact List.

The Sponsor will submit all required SAE Reports and Annual Progress Reports to the FDA as required by FDA or other local regulators.

All subjects with serious adverse events must be followed up for outcome.

Investigators **must** report to the Sponsor any serious adverse event (SAE) that occurs after the initial dose of study treatment, during treatment, or within 30 days of the last

dose of treatment on the SAE form provided by the Sponsor.

Investigators **should** report SAEs to their governing IRB following their governing-IRB's reporting requirements.

7.2 Expected Toxicities

For further information related to preclinical and clinical safety experience with ONC201, including expected adverse events, please refer to the Investigator's Brochure.

7.3 Adverse Event Characteristics

- **CTCAE term (AE description) and grade:**

The descriptions and grading scales found in the revised NCI Common Terminology Criteria for Adverse Events (CTCAE) version 5.0 will be utilized for AE reporting. All appropriate treatment areas should have access to a copy of the CTCAE version 5.0. A copy of the CTCAE version 5.0 can be downloaded from the CTEP web site http://ctep.cancer.gov/protocolDevelopment/electronic_applications/ctc.htm.

- **Attribution of the AE:**

- Definite – The AE is clearly related to the study treatment.
- Probable – The AE is likely related to the study treatment.
- Possible – The AE may be related to the study treatment.
- Unlikely – The AE is doubtfully related to the study treatment.
- Unrelated – The AE is clearly NOT related to the study treatment.

8. PHARMACEUTICAL INFORMATION

[figure not shown]
The investigational drug product is a hydroxypropyl methylcellulose (HPMC) capsule filled with ONC201 dihydrochloride salt, intended for oral administration. Each capsule of drug product contains 125mg of anhydrous ONC201 free base (equivalent to 148.8 mg of ONC201.2HCl). ONC201 capsules are manufactured using the following excipients: microcrystalline cellulose, sodium starch glycolate, and magnesium stearate.

The product is stored in a multi-dose container. The capsules are packaged in high-density polyethylene (HDPE) white opaque bottles, closed with an induction seal and capped with a white ribbed SecuRx® polypropylene (PPE) cap.

Each ONC201 bottle will be labelled in accordance with applicable regulatory requirements and will include the following minimum information:

- Name of study drug and strength
- Sponsor name
- Batch Number
- Storage condition
- Route of administration
- Applicable caution statement according to in-country requirements

8.1 Drug Substance Description

Compound Code(s)	ONC201•2HCl
Alternative Name(s)	ONC201 TIC10 NSC-350625
Chemical Name(s)	7-benzyl-4-(2-methylbenzyl)-1,2,6,7,8,9-hexahydroimidazo[1,2-a]pyrido[3,4-e]pyrimidin-5(4H)-one 2HCl
Molecular Formula	C ₂₄ H ₂₆ N ₄ O (free base) C ₂₄ H ₂₆ N ₄ O•2HCl (salt)
Molecular Weight	386.49 (free base) 459.41 (salt)
Molecular Structure	

8.2 Drug Product Description

8.2.1 Form

The investigational drug product is a hydroxypropyl methylcellulose (HPMC) capsule filled with ONC201 dihydrochloride salt, intended for oral administration. Each capsule of drug product contains 125mg of anhydrous ONC201 free base (equivalent to 148.8 mg of ONC201.2HCl). ONC201 capsules are manufactured using the following excipients: microcrystalline cellulose, sodium starch glycolate, and magnesium stearate.

The drug product will be packaged as 10 capsules per bottle. The capsules are filled into a 30cc high-density polyethylene (HDPE) white opaque bottle sealed with a 28 cc child-resistant SecuRx polypropylene (PPE) cap with a heat induction seal.

8.2.2 Storage and Stability

ONC201 should be stored at controlled room temperature (i.e., 15°C to 25°C [59°F to 77°F]), with excursions permitted to 30°C (86°F).

The investigator or qualified designee must confirm appropriate temperature conditions have been maintained during transit for all study drug received and must report and

resolve any discrepancies before use of the study drug.

